9.6 Protocol Deviations and Protocol Violations

9.6.1 Protocol Deviations

A "protocol deviation" is any change, divergence, or departure from the ethics committee approved protocol. Although every effort should be made to follow the protocol as written, it is common for studies to have protocol deviations. These deviations may result from human error, subject non-compliance, or confusing and/or ambiguous details. Protocol deviations may not alter the course of the study and do not pose a safety risk to the participant.

Examples include:

- Lab draws off schedule
- Office or phone visit off schedule
- Baseline laboratory values out of enrolment window
- Out of window or missed visit, or out of window or missed lab draw

9.6.2 Protocol Violations

A "protocol violation" is a protocol deviation that may affect the subject's rights, safety, or well-being and/or the completeness, accuracy and reliability of the study data. Major protocol deviations are considered substantive and adversely affecting one of the following:

- Rights or welfare of subjects

- Safety of subjects
- Willingness of subjects to continue with study participation
- Integrity of the research data

Examples include:

- Enrolment of ineligible subject
- Lack of valid consent form
- Failure to report an SAE
- Lapse in IRB approval
- Improper breaking of the blind
- Mishandled samples
- Materially inadequate record keeping
- Intentional deviation from the protocol, Good Clinical Practice, or government regulations by study personnel
- Subject repeated non-compliance with study requirements

9.6.3 Reporting of Protocol Deviations and Protocol Violations

When encountering a situation determined to be a protocol deviation, the site coordinator should complete a Protocol Deviation Assessment Form and submit it to the Coordinating Center. Protocol deviations do not need to be reported to the local ethics committee or the Emory IRB.

Protocol violations are **promptly** reportable. Prompt reporting is done by sending a Protocol Violation Assessment Form to the Coordinating Center and the local, site-specific ethics committee and should occur within 5 business days of event occurrence, or from when the Site Principal Investigator first learned about the event. The Emory ethics committee should be notified by the Coordinating Center within 10 business days of event occurrence, or from when the Site Principal Investigator first learned about the event. Protocol violations will be documented in the annual progress report to NIMH.

The Coordinating Center will log all protocol deviations and violations to identify possible trends that may indicate a substantive problem.

9.7 Non-Compliance

Non-compliance is the failure to follow national, state, or local regulations governing human subject research, institutional policies related to human subject research, or the requirements or determinations of the IRB. This may pertain to the principal investigator, research staff, or any member or component of the human research protection program.

Examples of non-compliance:

- Performing human subject research without first obtaining ethics committee approval or an ethics committee declaration of exemption
- Deviating from or violating the provisions of an ethics committee-approved protocol
- Failing to secure ethics committee approval of a protocol due for periodic continuing review prior to its expiration date
- Permitting a protocol's ethics committee approval to lapse without stopping all research-related activities and submitting a closing progress report to the ethics committee, or in the event of an overriding safety concern or ethical issue such that it would be in the individual subject's best interest to continue study participation, not arranging with the ethics committee to continue those activities

9.7.1 Serious Non-compliance

Serious non-compliance is non-compliance that creates an increase in risks to subjects, adversely affects the rights, welfare and safety of the research subjects or adversely affects the scientific integrity of the study. Willful violation of policies and/or federal regulations may also constitute serious non-compliance.

9.7.2 Continuing Non-compliance

Continuing non-compliance is a pattern of non-compliance that if allowed to continue is likely to increase risk to subjects, adversely affect the rights, welfare and safety of research subjects, or adversely affect the scientific integrity of the study.

9.7.3 Reporting of Serious Non-compliance

Serious non-compliance should be reported to the Research Coordinating Centre and the local, site-specific ethics committee within 5 business days of event occurrence, or from when the Site Principal Investigator first learned about the event. The MDRF and Emory ethics committees should be notified by the Research Coordinating Centre within 10 business days of event occurrence, or from when the Site Principal Investigator first learned about the event. Serious non-compliance that results in increased risks to subjects will be promptly reported to NIMH.

9.8 Criteria for Discontinuation of Intervention

Criteria for discontinuing the intervention **for a participant** include:

- 1) Moves away from proximity of the clinic research site
- 2) If the Lead Site Investigator finds the participant to be incompatible with the intervention. For example, if the participant is unable to engage in the intervention due to major stroke, is in a vegetative state, or cannot communicate with the care coordinator.
- 3) In-trial development or diagnosis of a major psychiatric illness (i.e. mania, bipolar disorder, schizophrenia, schizoaffective disorder), which may complicate treatment within a non-psychiatric health facility and/or greatly confound the health outcomes for the individual.

If any member of the local study team encounters a participant that meets any of the criteria for discontinuation, he/she must inform the Lead Site Investigator, who will report the incident to the Coordinating Center by completing a Participant Discontinuation Form.

Reasons for discontinuation of the study intervention **at a clinic research site** include:

- 1) Infrastructure unable to handle intervention (determined by quality monitoring).
- 2) Discontinuation recommended by steering committee or sponsor
- 3) Low-recruitment rate: less than 6 participants per month recruited

Discontinued participants will continue to be followed with their permission if the study intervention is discontinued at the clinic research site.

Discontinued participants will be followed up annually for 2 years from their date of enrollment for adverse events and serious adverse events/clinical outcomes of (1) death from any cause; (2) major macrovascular event: a composite of non-fatal MI, non-fatal stroke and death from any cardiovascular cause (based on investigator diagnosis); (3) microvascular events; and/or (4) major psychiatric event.

Secondary outcomes which will be followed include:

- 1) MI (non-fatal and fatal or revascularization procedure (angioplasty or CABG));

- 2) Stroke (non-fatal and fatal)
- 3) Requirement for renal replacement therapy (dialysis or transplantation);
- 4) Death from renal disease
- 5) Development of severe diabetes-related eye disease (defined as the requirement for retinal photocoagulation or similar treatment and development of diabetes-related blindness in either eye in a participant known not to have this condition at study entry); and
- 6) Major hypoglycemia episode (a hypoglycemic episode associated with transient central nervous system dysfunction without other apparent cause in which the individual was unable to treat him/herself and had help from another person to administer glucose or glucagon)
- 7) Acute hyperglycemia (e.g., DKA)
- 8) Amputation due to diabetes-related peripheral neuropathy and peripheral vascular disease
- 9) Major infection requiring hospitalization (e.g., pneumonia)
- 10) Any other health conditions/events.

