8	Follow-up visit with diabetes physician – If depressive symptoms or poor control persists , more intensive psychotherapies or doses.	Review of behavioral activation progress. Continued motivational enhancement and behavioral activation (guided activity).	Scheduled follow-up CC telephone calls.
10-16	As needed follow-up visits with CC (in-person or phone): review of control and adherence.	Review of behavioral activation progress. Continued motivation; behavioral activation.	
25-52	Monthly tailored follow-up (in-person or phone): support maintenance / relapse prevention.	Individual booster behavioral activation sessions.	

Each intervention participant will be enrolled in the integrated depression and diabetes care program (proactive follow-up and case reviews) for 12 months. All participants (intervention and control) will undergo outcomes assessments for months 0-36 (visits at 0, 6, 12, 18, 24 and 36 months following randomization). The focus of the 13-36 month assessments is to evaluate if effects of the intervention are sustained.

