6.2 Evaluation Schedule

The first visit is for participant screening and the second visit for confirming eligibility and documenting baseline status. Randomization will be computer-generated and CCs at each site will be notified of participants who are assigned to the intervention arm only. The CCs will then contact the intervention participants and schedule their initial and subsequent intervention visits directly with participants. Reviews by the team (diabetologist, psychiatrist, and CC) will happen weekly and the intensity of discussion on each participant will depend on CC and DS-EHR prompts and needs of the participants (well-controlled participants will require minimal discussion, while poorly-controlled participants may require more intensive discussion).

For the **intervention arm**: The CC will motivate and monitor participants' progress. The CC will update the participant's medications and labs plus PHQ-9 values in the DS-EHR and will provide a dashboard printout of participants' progress and suggested treatment plans and/or modifications for physicians to review at every case review meeting. The **usual care physician** will assess the participant and accept or modify the prompt (providing a reason if he/she chooses to modify the prompt). The case of this same participant will then be discussed, along with all other participants at the site weekly or bi-weekly case review meeting and the case review team will continue with or recommend modifications to the physician's and DS-EHR's care plan for the patient. If the case review team recommends modifications to the care plan these will be accepted or modified in a final review step by the usual care physician. The CC will update the participant and the DS-EHR system; address any barriers to care and motivate him/her to achieve risk factor management goals and confirm the next appointment dates. The CC will continue to facilitate the participant's adherence to appointments and self-management using DS-EHR reminders and phone calls.

For ALL participants: The blinded outcomes assessor at each site will independently contact all participants (intervention and control) to schedule post-randomization visits for study assessments. All other intermediate visits by the participants will be documented as they routinely are in participant's clinical case notes.

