For all randomized participants, the post-randomization follow-up period will be 36 months. The study staff at each site involved in executing the study procedures includes:

- **Lead Site Investigator/Co-investigator/Sub-investigator:**
 - Site PI: Oversee all trial-related procedures (recruitment, screening, enrollment, randomization, and follow-up of participants for medical evaluation)
 - Co-investigator or coordinator to support recruitment and retention activities
- **Blinded Outcomes Assessor:**
 - **Screening and Outcomes Assessments:** a research physician or nurse that will perform screening evaluations, baseline and six-monthly history and physical examination and enters data into DS-EHR system, which randomizes participants into trial arms.
- **Care Coordinator:**
 - Motivates intervention participants to self-manage and self-monitor their conditions;
 - Monitors intervention participants and enters PHQ-9 and blood testing (glucose, HbA1c, BP, and cholesterol levels) data from clinic report forms regularly into DS-EHR and follows prompts regarding case reviews
 - Coordinates with diabetologist and psychiatrist to conduct case review meetings for intervention participants on a weekly or bi-weekly basis

- Supplies the intervention participants' management plans (generated from the DS-EHR) to study physicians at case review meetings
- Conveys any treatment plan changes to intervention participants and continues monitoring until 36 months post-randomization
- **Usual Care Physicians (diabetes or primary care physicians at each site):**
 - Routine care for participants, whether control or intervention arm
 - Attend continued education training on managing diabetes and depression
 - For intervention participants, assess output prompts from DS-EHR system and accept or reject implementation of this care plan, providing reasons for any rejection
- **Case Review Specialists (psychiatrist and diabetologist at each site):**
 - Discuss all participants' cases in the intervention arm on a weekly or bi-weekly basis
 - Recommend treatment maintenance or changes based on the outputs of the DS-EHR and clinical judgment

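### Section 9.8 makes slow recruitment a reason to stop the intervention at a site, so as worded it can cut short the 12-month programme for participants already randomised there (minor)

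*Combined protocol and SAP*

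**What the plan says.** Section 9.8 has two lists. One gives criteria for ending the intervention for an individual participant. The other gives reasons for ending the study intervention at a clinic research site. The site list has three items: inadequate infrastructure, a recommendation by the steering committee or sponsor, and "Low-recruitment rate: less than 6 participants per month recruited".

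The text then turns to people at such a site: "Discontinued participants will continue to be followed with their permission if the study intervention is discontinued at the clinic research site". A further sentence sets a schedule for them: "Discontinued participants will be followed up annually for 2 years from their date of enrollment for adverse events and serious adverse events/clinical outcomes".

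Section 5.2 fixes the length of the programme: "Each intervention participant will be enrolled in the integrated depression and diabetes care program (proactive follow-up and case reviews) for 12 months". It also says "All participants (intervention and control) will undergo outcomes assessments for months 0-36". Section 6.2 adds "For all randomized participants, the post-randomization follow-up period will be 36 months" and "The blinded outcomes assessor at each site will independently contact all participants (intervention and control) to schedule post-randomization visits for study assessments".

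Section 9.3 has sites report recruitment every three months, but 9.8 does not link its threshold to those reports.

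**The concern.** Recruitment speed is a reason to stop enrolling at a site. It says nothing about whether the programme is safe, deliverable or useful for someone already randomised. Yet what item 3 stops is the intervention, and the following sentence treats people at the site as discontinued. No sentence elsewhere says that they finish their 12 months.

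If the reason were used, some intervention participants would get a shortened programme because of their site's enrolment rate, while controls would lose nothing. Under intention to treat, that dilutes the 24-month difference.

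The threshold is also hard to apply. With no stated period, it could be read month by month. Once enrolment closes, every site recruits nobody and literally meets it, although late enrollees are still in the programme.

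**Working it through.** **1. Reproduce the plan's sample size.** Inputs from section 4.1: 30% vs 15%, 80% power, continuity-corrected two-sample test of proportions. Alpha is not stated; two-sided 5% is assumed.

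- Uncorrected: n = [1.96·√(2·0.225·0.775) + 0.8416·√(0.30·0.70 + 0.15·0.85)]² / 0.15² = 120.5 per arm.
- Corrected: (120.5/4)·[1 + √(1 + 4/(120.5·0.15))]² = 133.5, so 134 per arm and 268 in total.
- With 20% loss: 268/0.8 = 335.

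Both figures match the plan.

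**2. Power before any dilution.** Section 4.1 aims for 360; sections 1 and 4.2 give 400. Evaluable per arm: 360·0.8/2 = 144, or 400·0.8/2 = 160.

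Power = Φ{[d·√n′ − 1.96·√(2·p̄·(1−p̄))] / √(p₁q₁ + p₀q₀)}, where d is the difference and p̄ the mean of the two rates. With the continuity correction, n′ = n − 2/d + 1/(n·d²); without it, n′ = n.

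At n = 144 and d = 0.15, n′ = 144 − 13.33 + 0.31 = 130.98 and power is Φ(0.963) = 83%. Uncorrected power is 87%.

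**3. One stopped site with 30 participants.** The 30 is an assumption, because the documents give no expected site rate. The overall total is assumed still to be reached. With 1:1 allocation, 15 of 180 intervention participants (8.33%) are affected, and controls stay at 15%.

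| Benefit kept by those affected | Difference (points) | Power, 144 per arm, corrected | Uncorrected |
|---|---|---|---|
| Not affected | 15 | 83% | 87% |
| Half | 15·(1 − 0.0417) = 14.4 | 80% | 84% |
| None | 15·(1 − 0.0833) = 13.75 | 77% | 81% |

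With 30 of 400 (7.5%) and 160 per arm, the differences are 14.4 and 13.9 points, and corrected power goes from 87% to 85% or 82%.

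**4. The same question by programme time lost.** Assume a site enrols 5 per month evenly and 1:1, and that benefit is proportional to time in the programme. Planned programme time is 180·12 = 2,160 months.

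- Stopped at month 6: 15 intervention participants lose 9 months on average, which is 135 months or 6.25%. The difference is 14.1 points; power is about 79% corrected and 82% uncorrected.
- Stopped at month 12 or later: the loss levels off at 2.5·72 = 180 months (8.33%), because earlier enrollees have finished. The difference is 13.75 points, as in the last row above.
- At 5.9 per month, just under the threshold, the plateau is 2.95·72 = 212.4 months (9.8%). The difference is 13.5 points; power is 75% corrected and just under 80% uncorrected.

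Proportional loss probably overstates the effect, since Table 2 in section 5.2 describes weeks 25–52 as "Monthly tailored follow-up (in-person or phone): support maintenance / relapse prevention".

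**5. How often a month-by-month reading would be met.** This is illustrative only. It assumes four equal sites (360/4 = 90 each) and Poisson recruitment.

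| Site average per month | Months to reach 90 | P(below 6 in a given month) | P(at least one such month) |
|---|---|---|---|
| 6 | 15 | 45% | >99.9% |
| 7.5 | 12 | 24% | 96% |
| 10 | 9 | 7% | 46% |

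Under these assumptions, a site with an average at or above the threshold would often meet a single-month criterion.

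**The case against.** The strongest reply is that 9.8 lists reasons, not triggers. It names no decision-maker and no automatic action. Recruitment is also watched through the 3-monthly site reports (9.3) and by the data safety and monitoring board (9.1). A reader might infer that one slow month shuts a site down; the documents do not say that. This stands, and it means the effect may be zero.

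Enrolment closure is also a plausible intent. Recruitment rate appears only in the site-level list, section 5.2 promises 12 months without exception, and the sentence about discontinued participants also serves the infrastructure item, where stopping the programme is natural. That stands as a point about intent. It does not remove the ambiguity, because no text limits item 3 to new enrolment.

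A reader might also infer that participants would lose their care. They would not: section 6.2 has usual care physicians treat both arms and attend training on diabetes and depression. What would go is the added programme.

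Finally, a reader might infer from the annual, two-year, event-based schedule in 9.8 that 24-month outcome data would be lost at a stopped site. The better reading is the opposite. Section 9.8 itself says follow-up continues, sections 5.2 and 6.2 give all randomised participants assessments to 36 months with the blinded assessor contacting everyone, and section 7 has everyone approached at each time-point unless they withdraw. Only the link between the two schedules is left unstated.

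On size, the continuity correction belongs to the sample-size calculation. Section 10.1 plans an unadjusted difference and logit models and mentions no correction, so the uncorrected column may be closer to the actual analysis. There the 80% target is essentially kept. The planned per-protocol and site-by-treatment analyses could examine a stopped site, though with limited precision.

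**Conclusion.** The point holds as a minor defect of wording. Section 9.8 attaches a recruitment threshold to stopping the intervention rather than enrolment, and, followed as written, it can shorten the 12-month programme for people already randomised.

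The effect is conditional and modest: nothing if the reason is unused, and about 0.6 to 1.3 points of the planned 15 if one site of about 30 participants is stopped. These figures rest on an assumed number affected, assumed retained benefit and an assumed 5% alpha. They do not show a material threat to the trial's validity. The documents do not support reading 9.8 as an automatic stop, a loss of all care or a loss of primary outcome data.

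**What to change.** Take item 3 out of the list for discontinuing the intervention and make it an enrolment rule. Low recruitment, averaged over a stated period within the recruitment phase (the 3-monthly reports in 9.3 would serve), closes the site to new screening. State that participants already randomised there complete the 12-month programme and all scheduled outcome visits. As an editorial note, add that the annual event follow-up in 9.8 is in addition to those visits.

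This is a short amendment to one section, with no change to sample size or analysis. The small downside is that coordinator time, already planned in section 5.2, continues at a slow site until its participants finish. Items 1 and 2 still allow the intervention at a site to be stopped for other reasons.

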9.9 Data Safety

The respective site coordinators and all study staff at each participating clinic research site will complete training in the protection of human subjects, including training in data handling and confidentiality. The project managers will administer all transfers, organization, storage, and back-up of study data. They will work closely with participating clinic investigators to ensure all data is secured and any edits can be tracked using: password-protected access; automated edit tracking; audit trails; validation tools for data-entry (split screen views); and encrypted transfer facilities.

10 Data Analysis

10.1 Primary and Secondary Health Outcomes

Participants in both arms will be invited for 6-monthly assessments [0, 6, 12, 18, 24 and 36 month time-points] for blinded outcomes assessors. Data for health outcomes analyses will include demographic (age, sex, marital status, education, occupation, income, migration status), anthropometric data (height, weight, waist circumference), depression (SCL-20 and PHQ-9), and risk factor levels (fasting blood glucose, HbA1c, BP, lipid levels, and tobacco use). Data regarding patient-centered outcomes such as treatment satisfaction, quality of life and utility [reflects participants' judgments regarding different health states on a continuum from 0.0 (representing death) to 1.0 (perfect health)] will be collected using the Summary of Diabetes Self Care Activities, Diabetes Treatment Satisfaction Questionnaire, and Health Utilities Index-3.

Data Analysis: Recruitment and retention of trial participants will be assessed by examining: number screened, number eligible to be randomized, number enrolling in the study, and dropout from regular testing at the completion of 36 months. We will test for differences in baseline characteristics to assess randomization using appropriate statistical tests for sample proportions [χ^2] or means [t-tests]. Between-group differences in primary and secondary outcomes will be assessed at 12, 24 and 36 months, using the following indicators:

- **Primary Outcome:** At each time-point, we will test the unadjusted difference in the proportion achieving the primary outcome, which jointly evaluates depressive symptoms and CVD risk reduction.

- Secondary Outcomes:** Given the objective of assessing the cumulative benefits of a multi-component intervention, a “common treatment effect” will be tested on all four main targets [SCL-20, HbA1c, SBP, LDL-c] jointly using a scaled marginal model.¹ Each target, measured continuously, is scaled by its standard deviation and a single parameter is estimated representing the “common effect” on all targets. The advantage of this approach is that all targets can be measured continuously, thereby improving power, and a “common effect” in standard deviation units is produced. Katon¹⁸ used this approach in a similarly designed trial [the model is estimable using the SAS PROC GENMOD procedure²⁶ described by Roy].¹
- Additional secondary outcomes that will be evaluated include: (1) a measure of “common effect,” i.e. whether the intervention had a similar beneficial effect on all four main targets [SCL-20, HbA1c, SBP, LDL-c];¹ proportion of participants achieving all 3 CVD risk factor targets; (2) mean reductions in four main targets [SCL-20 score; HbA1c; SBP; LDL-c]; (3) proportion of participants achieving treatment targets or significant reductions in individual risk factors (depression control [$\geq 50\%$ reduction in SCL-20]; glycemic control [HbA1c $\leq 7.0\%$ **or** $\geq 0.5\%$ reduction]; BP control [SBP ≤ 130 mmHg **or** ≥ 5 mmHg reduction]; lipid control [LDL ≤ 100 mg/dl **or** ≥ 10 mg/dl reduction]; (4) mean utility, quality of life, and depression- and diabetes-specific patient satisfaction scores; and (5) mean health expenditures and within-trial cost-utility.

All analyses will be conducted with both intention to treat (ITT) and per protocol analytical approaches. All treatment effects (primary and secondary outcomes) will be assessed using multivariate regression models adjusted for baseline characteristics. Generalized linear models will be estimated with appropriate link functions and error distributions for each outcome [e.g., logit models for dichotomous outcomes]. Heterogeneity in treatment effects across sites will be tested with interaction terms between site and the treatment variable. Similarly, heterogeneity in treatment effect by baseline age, gender, socioeconomic status, SCL-20, HbA1c, SBP, and LDL-c will also be evaluated. Robust standard errors will be estimated to account for within-site clustering [design effects].

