1.1 Primary Outcome

The sustained (24 month) difference in the proportion of trial participants in each arm achieving combined improvements in depressive symptoms and CVD risk factors ($\geq 50\%$ reduction in the Symptoms Checklist-20 items [SCL-20] score AND one or more of the following: $\geq 0.5\%$ reduction in HbA1c, ≥ 5 mmHg reduction in SBP, or ≥ 10 mg/dl reduction in LDL-c).

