4.1 Sample Size

The study is powered on between-arm differences in the proportion achieving the primary outcome [*combined depression and CVD risk factor improvements* ($\geq 50\%$ reduction in SCL-20 **and** ≥ 1 of: $\geq 0.5\%$ reduction in HbA1c **or** $\geq 5\text{mmHg}$ reduction in SBP **or** $\geq 10\text{mg/dl}$ reduction in LDL-c)] at 24 months post-randomization. The sample size estimation is guided by: (1) studies in India^{14,15} and elsewhere^{16,17} showing that $<50\%$ of all people with diagnosed diabetes routinely achieve single or multiple CVD risk factor targets; and (2) published results by Katon¹⁸ demonstrating a 30% between-group absolute difference [60% (TEAMCare) vs. 30% (usual care)] in proportions of subjects achieving $\geq 50\%$ reduction in SCL-20 score at 12 months and 15% absolute difference [37% vs. 22%] in the proportion of subjects achieving significant reductions or target control for all three CVD risk factors [HbA1c, SBP, LDL-c]. It is anticipated that a 15% absolute difference [30% of intervention arm participants will achieve combined and sustained reductions in depressive symptoms **plus** ≥ 1 CVD risk factor at 24-months post-randomization, compared to 15% of usual care participants]. Using a two-sample test of equality of proportions and a normal approximation with a continuity correction in Stata Version 12.0., we calculated that $n=268$ provides 80% power, and $n=335$ allows additional 20% for loss to follow-up. The aim is to recruit an enhanced sample of 360 participants, assigned equally to the two arms with the goal of randomizing 120 participants across the four clinic sites.

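### Section 10.1 gives two unranked analyses of the primary outcome; the adjusted one names no risk difference as its effect measure and uses standard errors clustered on four sites

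*Combined protocol and SAP*

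**What the plan says.** Section 1.1 defines the primary outcome on the risk-difference scale, as the "difference in the proportion of trial participants in each arm" reaching the composite response at 24 months. Section 4.1 sizes the trial for the same contrast, "Using a two-sample test of equality of proportions and a normal approximation with a continuity correction".

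Section 10.1 then gives two rules for analysing it:

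- The primary-outcome bullet, which applies at 12, 24 and 36 months: "we will test the unadjusted difference in the proportion achieving the primary outcome".
- The closing paragraph: "All treatment effects (primary and secondary outcomes) will be assessed using multivariate regression models adjusted for baseline characteristics". It calls for generalized linear models with suitable links and gives "logit models for dichotomous outcomes" as an example. It adds: "Robust standard errors will be estimated to account for within-site clustering".

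The same paragraph also says: "All analyses will be conducted with both intention to treat (ITT) and per protocol analytical approaches".

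No sentence says which of these results is primary. The adjustment covariates are not listed. Site appears through an interaction test and the robust standard errors, but is not named as a main-effect covariate.

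**The concern.** The second rule names the primary outcome in brackets, so it cannot be confined to the secondary outcomes. Two methods times two analysis sets gives 2 × 2 = 4 candidate results at 24 months. The plan does not say which one decides the trial.

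The two methods need not report the same quantity. The first gives a difference in proportions, which is what Section 1.1 asks for. A logit model reports a conditional odds ratio unless it is converted, and the plan describes no conversion.

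The adjusted rule is also loose where looseness matters. Its covariates are open, and Section 10.1 plans significance tests of baseline differences, so choosing covariates after seeing those tests is not excluded. Its standard errors rest on four clusters, too few for the usual large-sample approximation.

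At stake are a primary conclusion that could depend on which line of the report is read, some power available from data already collected at baseline, and an unreliable standard error if the adjusted rule is followed literally.

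**Working it through.** **Inputs from the documents.** Planning rates of 30% and 15%, equal allocation, 80% power, continuity correction and 20% loss to follow-up (Section 4.1); four sites and individual randomization (Section 3); no stratification stated (Section 4.5). Alpha is not stated. I assume 0.05 two-sided, which reproduces the stated total; a one-sided 0.05 test with the correction gives 216.

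**The plan's own figure.** With p̄ = 0.225 and d = 0.15:

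n = [1.960·√(2·0.225·0.775) + 0.8416·√(0.30·0.70 + 0.15·0.85)]² / 0.15² = (1.1575 + 0.4889)² / 0.0225 ≈ 120.5 per arm

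Continuity correction: (n/4)·[1 + √(1 + 4/(n·d))]² = 30.12 × 2.105² ≈ 133.5, so 134 per arm and 268 in total. Then 268 / 0.80 = 335. Both stated figures reproduce exactly, and they are built on the unadjusted test.

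**Effect measures.** At the planning rates the unadjusted rule targets 0.30 − 0.15 = 15 points. The corresponding odds ratio before adjustment is (0.30/0.70)/(0.15/0.85) = 2.43. The conditional odds ratio changes again as prognostic covariates enter.

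**Operating characteristics.** Simulation with N = 268, four equal sites and 4,000 trials per cell. The comparison is a pooled z-test without continuity correction against a logit with arm, one baseline covariate and site terms. A third analysis drops the site terms and clusters the standard errors on site, with a normal reference. The covariate's log odds ratio per SD (0, 0.5, 1.0) and the site SD on the logit scale (0, 0.5) are assumptions, because the documents give neither. Results in per cent:

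| Covariate | Site SD | Type I: unadjusted | Type I: adjusted | Type I: either of these two | Type I: site-clustered | Power: unadjusted | Power: adjusted | Disagree at 30% vs 15% |
|---|---|---|---|---|---|---|---|---|
| 0 | 0 | 5.1 | 5.1 | 5.3 | 15.0 | 84.2 | 84.0 | 1.2 |
| 0 | 0.5 | 4.8 | 5.1 | 5.3 | 14.9 | 86.4 | 86.2 | 0.9 |
| 0.5 | 0 | 5.1 | 5.1 | 5.9 | 14.1 | 84.9 | 85.9 | 3.4 |
| 0.5 | 0.5 | 4.8 | 5.2 | 5.8 | 15.0 | 85.0 | 86.2 | 3.6 |
| 1.0 | 0 | 4.6 | 4.8 | 6.4 | 14.0 | 84.8 | 89.2 | 7.6 |
| 1.0 | 0.5 | 4.2 | 5.0 | 6.1 | 14.5 | 85.8 | 89.2 | 6.7 |

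Simulation error (95%) is about 0.7 points on a 5% type I error and 1.1 points on power. By formula, unadjusted power at 268 is 84.0% without the continuity correction and 80.2% with it, so the table compares like with like only for an uncorrected test.

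A separate simulation at the same N gave a power gain of about 0–4 points, disagreement in about 2–8% of trials, type I error of about 5–7% if either result may count, and about 13–14% for the site-clustered errors. The ranges in the verdict cover both sets.

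**The case against.** The strongest reply is that the plan already points to one primary test. The unadjusted comparison carries the primary-outcome label, Section 1.1 asks for a difference in proportions, and Section 4.1 sizes the trial with a two-sample test of proportions. An unadjusted primary test followed by adjusted models is a common pairing. This stands as an inference about intent, but the plan never states it. Section 10.2, by contrast, does rank its economic perspectives into a base case and secondary analyses.

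Three stronger readings are tempting, and the documents do not support them:

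- A reader might infer that the unadjusted test is wrong because it leaves out baseline values and site. Under individual randomization with no stated stratification it is valid; its simulated type I error is 4.2–5.1%. Baseline values already enter the response, which is a change from baseline. The cost of omitting them as covariates is power.
- A reader might infer that the plan inflates type I error by offering two chances of success. The excess over 5% arises only if success may be claimed on either result, which the plan does not propose. It reaches 6–7% only with a strongly prognostic covariate.
- A reader might infer that the adjusted rule commits the trial to an odds ratio. Logit is only an example, and a logit fit can be standardised to a risk difference. The accurate criticism is that the effect measure is not named.

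It can also be said that one ranking sentence would be enough. That would settle the ambiguity. It would not repair the clustered standard errors in the adjusted analysis, nor recover the power.

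**Conclusion.** The concern holds in this form: Section 10.1 gives two unranked rules for the primary outcome. The unadjusted rule is valid and agrees with the sample-size method, but forgoes about 0 to 4.5 points of power at N = 268. The adjusted rule does not name the Section 1.1 risk difference as its effect measure. Its site-clustered standard errors give about 13–15% type I error against a nominal 5% if referred to a normal distribution; the plan states no reference distribution.

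If either result could be read as primary, type I error is about 5–7%, and the two analyses disagree on significance in about 1–8% of trials under 30% versus 15%.

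These sizes rest on two-sided alpha of 0.05, on assumed covariate and site strengths, and on one simulated covariate standing in for the four baseline targets. The lack of ranking and the unnamed effect measure rest on none of these. This is worth correcting, but it does not make the planned unadjusted comparison invalid.

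**What to change.** Name one primary analysis in Section 10.1: the 24-month composite in the intention-to-treat set, by logistic regression on arm, site as a fixed effect, and baseline SCL-20, HbA1c, SBP and LDL-c. Convert it by marginal standardisation to an adjusted risk difference with a 95% confidence interval (delta method or bootstrap), so that it estimates the Section 1.1 quantity. Do not use site-clustered standard errors for this analysis; the fixed effect handles site. State alpha and sidedness.

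Label the unadjusted difference, the per-protocol analysis and the 12- and 36-month comparisons as supportive.

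The cost is SAP wording and slightly more complex estimation. All the covariates are already collected at the baseline visit (Table 4). The stated 268 and 335 stand, because they were derived for the unadjusted test and the adjusted analysis had about the same power or more in these simulations. If the sponsor prefers to keep the unadjusted test as primary, the ranking sentence, the analysis set and the change to the clustered standard errors are still needed.
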